#### **15.1 DEFINITIONS**

Adverse Event (AE): Any untoward medical occurrence, unintended disease or injury, or untoward clinical signs (including abnormal laboratory findings) in subjects, users, or other persons, whether or not related to the investigational medical device and whether anticipated or unanticipated.

- 1. This definition includes events related to the investigational medical device.
- 2. This definition includes events related to the procedures involved.
- 3. For users or other persons, this definition is restricted to events related to investigational medical devices.

Adverse Device Effect (ADE): Adverse Event related to the use of an investigational medical device.

1. This definition includes adverse events resulting from insufficient or inadequate instructions for use, deployment, implantation, installation, or operation, or any malfunction of the investigational medical device.

2. This definition includes any event resulting from use error or from intentional misuse of the investigational medical device.

**Device Deficiency:** Inadequacy of a medical device with respect to its identity, quality, durability, reliability, usability, safety, or performance. Device deficiencies include malfunctions, use errors, and inadequacy in the information supplied by the manufacturer including labeling.

Serious Adverse Device Effect (SADE): Adverse Device Effect that has resulted in any of the consequences characteristic of a serious adverse event.

Serious Adverse Event (SAE): Adverse Event that led to any of the following:

- (a) death;
- (b) serious deterioration in the health of the subject, that resulted in any of the following:
  - i. a life-threatening illness or injury, or
  - ii. permanent impairment of a body structure or a body function including chronic diseases, or iii. inpatient or prolonged hospitalization, or

iv. medical or surgical intervention to prevent life-threatening illness or injury, or permanent impairment to a body structure or a body function,

(c) fetal distress, fetal death or a congenital physical or mental impairment or birth defect.

NOTE: Planned hospitalization for a pre-existing condition, without serious deterioration in health, is not considered a serious adverse event.

**Unanticipated Adverse Device Effect (UADE):** Any serious adverse effect on health or safety or any lifethreatening problem or death caused by, or associated with, a device, if that effect, problem, or death was not previously identified in nature, severity, or degree of incidence in the investigational plan or application (including a supplementary plan or application), or any other unanticipated serious problem associated with a device that relates to the rights, safety, or welfare of subjects.

NOTE: An anticipated serious adverse device effect (ASADE) is an effect which by its nature, incidence, severity, or outcome has been identified in the risk assessment.

# **15.2 REPORTING**

#### **15.2.1 Investigator Responsibilities**

All Serious Adverse Events (SAEs), Serious Adverse Device Effects (SADEs, both Anticipated or Unanticipated), including any Device Deficiency that could have led to an SADE, must be reported to the Sponsor or designee within 24 hours of knowledge of the event. It is the responsibility of the Sponsor or designee to report the occurrence of any SAE, SADE, and/or UADE to the IRB according to IRB guidelines and national laws and regulations.

The Principal Investigator or designee will contact all subjects who record an adverse event or potential adverse event in ePRO. The subject will be asked to provide the following for the event:

- Any further details about the event or the subject's experience using the investigational product not already recorded in ePRO, if deemed necessary by the investigator Outcome, with options to include:
  - Ongoing/Not Resolved/Not Recovered
  - Recovering/Resolving
  - O Recovered/Resolved

- Recovered/Resolved with Sequelae
- Unknown
- Resolution date if the outcome is reported as recovered/resolved, with or without sequelae 

   Any treatments taken for the event and/or any actions taken to receive or schedule treatment
   Action taken with the study treatment in response to the event, with options including: 

   No action
  - Discontinuation of study treatment
  - Temporary halt of the study treatment; if temporary halt, the subject will be asked if the event resolved or continued after stopping the study treatment and the dates when treatment was paused.
- Relationship of the event to the use of the investigational device, reported as either Related or Not related

The investigator will review all of the reported information from the subject and separately record their causality using the following options:

- Not Related: An AE which cannot be attributed to the study device.
- Unknown Relationship: The relationship of the AE to the device cannot be determined.
- Possible: The AE occurs within a reasonable time sequence to study device usage and there is some evidence to "possibly" suggest a causal relationship. However, the influence of other factors such as underlying disease, concomitant medications, or concurrent treatment may have contributed to the event.
- Probable: The temporal sequence between the device use and the event is such that the relationship is likely or subject's condition or concomitant therapy could have caused the AE.
- Definite: The AE occurs in a plausible time relationship to study device usage and cannot be explained by any concurrent disease or other devices, drugs or chemicals.

Additionally, the investigator will record in ePRO if the AE meets the definition of a Serious Adverse Event (SAE) as per the definition in Section 15.1.

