If the screened subject's data is within the acceptable range for the BDI-II, the subject will advance to scheduling a meeting with a clinician from the investigative team. Via teleconference, the clinician will administer the M.I.N.I. assessment and the Diagnostic and Statistical Manual of Mental Disorders (DSM-5) evaluation.

If the clinician identifies that the subject's results do not meet both M.I.N.I. and DSM-5 criteria for moderate to severe MDD, the subject will be notified that they are no longer eligible for study participation. Additionally, during the live interview, the clinician may deem the subject a screen failure should they no longer meet all inclusion criteria or meet any exclusion criteria.

If the clinician diagnoses the subject with moderate to severe MDD based on the results of the M.I.N.I. and DSM-5 assessments, and determines that the subject meets all other eligibility criteria, the subject will be prescribed study treatment by the clinician and be randomized to a study treatment arm (sham device or active treatment device). Only eligible subjects will be enrolled in the study, randomized to a treatment arm, and receive an investigational device shipped directly to them by an unblinded Sponsor designee.

Prior to starting self-administered therapy with the FW-200 sham or active device, subjects will review an online device training video and undergo a live device and ePRO training with investigative staff. The day after successfully completing live training with investigative staff, subjects will begin self-administered therapy twice per day, one 20-minute session after waking for the day and one 20-minute session before going to bed. Each day of study therapy, subjects will confirm in ePRO that they completed both treatment sessions for the day. Subjects will also be asked if there have been any changes to their medications or health status within the past 24 hours. This will be captured as free text to allow subjects to describe any positive or negative (adverse events) experiences during study therapy.

At the following time points, subjects will retake the BDI-II, PHQ-9, and QIDS-SR assessments:

- Week 1 (Day 7 of therapy)
- Week 2 (Day 14 of therapy)
- Week 4 (Day 28 of therapy)

For the Week 1 and Week 2 evaluations, subjects will have 2 additional days to complete the assessments. For the Week 4 evaluation, subjects will have 5 additional days to complete the assessments. Should a

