# 7.2 SUBJECTS

# 7.2.1 Inclusion Criteria for Subject Selection

Subjects will need to meet all the following inclusion criteria:

- 1. Age 21-65 years and a resident of the United States of America
- 2. Meets DSM-5 diagnostic criteria for moderate to severe Major Depressive Disorder
- 3. Baseline BDI-II score between 20 and 63, inclusive (in moderate to severe range)
- 4. Able to receive packages to their home via UPS/FedEx/USPS or other delivery service
- 5. Willing and able to send and receive study related text messages on an internet capable mobile device throughout the duration of the study
- 6. Owns and uses a personal, verifiable email address
- 7. Able to commit to two (2) 20-minute treatment sessions per day for 4 weeks, one treatment upon waking for the day and one treatment before going to bed
- 8. Willing to abstain from use of recreational drugs, hypnotics, steroids, and/or marijuana products through study completion
- Willingness to not initiate treatment for a mental health issue during the course of the study 10.
   Fluent in English

Version 5.0 08-Jun-2022

- 11. Sexually active females of childbearing potential willing to commit to practicing at least one or more of the following methods of contraception during the study: intrauterine device (IUD), barrier method in combination with a spermicide, oral/hormonal contraception, or abstinence
- 12. In the opinion of the investigator, able to comply with study requirements and complete the study

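### The Probable causality grade in Section 15.2.1 can be met by a plausible non-device cause, which contradicts the Possible and Definite grades on either side of it

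*Combined protocol and SAP*

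**What the plan says.** Section 7.1.1 has subjects report changes in health and medication each day in ePRO: "This will be captured as free text to allow subjects to describe any positive or negative (adverse events) experiences during study therapy". Under Section 15.2.1 the Principal Investigator or a designee then contacts each subject who records an event. Relatedness is collected twice. The subject answers Related or Not related. The investigator reviews all the reported information and separately picks one of five grades: Not Related, Unknown Relationship, Possible, Probable or Definite.

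The definitions that matter here, all in Section 15.2.1, are:

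- *Possible*: "The AE occurs within a reasonable time sequence to study device usage and there is some evidence to" suggest, tentatively, a causal link. A caveat follows that "underlying disease, concomitant medications, or concurrent treatment may have contributed to the event".
- *Probable*: either the timing makes the relation likely, or the subject's "condition or concomitant therapy could have caused the AE".
- *Definite*: plausible timing, and the event "cannot be explained by any concurrent disease or other devices, drugs or chemicals".
- *Unknown Relationship*, lower on the scale: "The relationship of the AE to the device cannot be determined".

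The safety endpoint is the rate of related AEs: device related in Section 1.3, device and procedure related in Section 6.4. Neither section says whether the subject's answer or the investigator's grade is used, or which grades count as related.

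**The concern.** From *Possible* to *Definite*, a competing explanation should weigh more and more against the device. It does so at both ends of that range. At *Probable*, in the middle, it becomes a sufficient reason for the grade. The sentence is complete, shows no sign of redaction or extraction damage, and is not corrected elsewhere in the protocol.

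The definition is an operative rule. Relatedness is the substance of the only safety endpoint, and Section 15.1 defines adverse device effects and serious adverse device effects by it. The second route is also not far-fetched in this trial: subjects have depression by inclusion, stable nervous-system medication is allowed (Section 7.2.2, criterion 5), and Section 15.3 expects AEs that arise from the patient population and its other treatments. An investigator who follows the text could therefore record as probably device-related an AE that the illness or a medicine explains.

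**Working it through.** The plan gives no figure on this point, so there is nothing numerical to reproduce. The check is a reading of the grades side by side.

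**Conditions**

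- L: timing makes a relation to the device likely.
- T: timing is reasonable.
- E: there is some evidence that suggests a causal link to the device.
- C: the subject's illness or other treatment could have caused the AE.

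**Definitions as written**

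| Grade | Requires | Role of C |
|---|---|---|
| Possible | T and E | caveat only |
| Probable | L or C | sufficient alone |
| Definite | plausible timing and no other explanation | must be absent |

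**Case 1: C true, E false, L false.** *Possible* fails for want of E. *Definite* fails because another explanation exists. *Probable* is met through C. *Not Related* and *Unknown Relationship* also remain open, depending on the facts.

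**Case 2: T, E and C true, L false.** *Possible* is met, and so is *Probable* through C. The grades do not exclude each other, and the caveat that should hold the AE at *Possible* also qualifies it for the higher grade.

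**Alternative parse.** The sentence can be read so that the timing clause governs both routes: the timing is such that either the relation is likely or the illness or other treatment could be the cause. In case 1, timing compatible with the illness as cause then still yields *Probable*, and E is still missing for *Possible*. The inconsistency remains.

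**Route to the endpoint.** An effect on the related-AE rate needs two conditions that the documents do not state: the endpoint uses the investigator's grade, and *Probable* counts as related. If both hold, the AEs that could be added are:

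- those otherwise graded *Not Related* or *Unknown Relationship*, if *Possible* also counts as related;
- those, and also AEs otherwise graded *Possible*, if *Possible* does not count.

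**Effect on the comparison of arms.** Let a and b be the correctly related counts in two arms of equal size, and let k non-device AEs be added to each. The difference is (a + k) − (b + k) = a − b, unchanged. For a and b unequal and above zero, the ratio (a + k)/(b + k) lies closer to 1 than a/b. Both rates rise, the absolute contrast stays, and the relative contrast shrinks. No value of k can be given, because the documents hold no AE rate or grade distribution for this trial.

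**The case against.** The strongest reply is that the wording permits misgrading but does not force it. The five grades are options for one judgement made after all the information is reviewed. For an AE with another cause and nothing pointing to the device, *Not Related* or *Unknown Relationship* fits better, and a sensible investigator would choose it. That is fair and limits the consequence. It does not repair the definition, because the investigator must then set the written rule aside.

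The second reply is that the path to the endpoint is not established, since the subject's binary answer is also collected and Section 8 leaves further analysis detail to a standalone SAP, which is not among the documents. This stands. The effect on the endpoint is therefore conditional, and the mapping belongs in the fix.

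Third, the safeguards are real. The Principal Investigator is blinded, and safety data are compared by arm (Section 6.1). Serious AEs go to the Sponsor within 24 hours (Section 15.2.1), unanticipated adverse device effects have their own definition (Section 15.1), and study success rests on the primary efficacy test (Section 8.3). The error runs towards over-attribution, so it does not hide harm from the device.

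A reader might infer two stronger claims that the documents do not support:

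- *The second route reaches every AE in the trial.* Inclusion criterion 2 ("Meets DSM-5 diagnostic criteria for moderate to severe Major Depressive Disorder") covers all subjects, but the route asks whether the illness could have caused the particular AE. Section 5.2 lists skin irritation, shocks and burns among the device risks, and depression does not plausibly explain these. A count of subjects is not a count of affected AEs.
- *Timing cannot discriminate because "subjects will begin self-administered therapy twice per day".* Frequent use does make recent exposure common. But Section 15.2.1 also collects the resolution date, any pause in treatment with its dates, and whether the AE resolved on stopping. A judgement on timing can use all of these.

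**Conclusion.** The inconsistency is real on either reading of the sentence: an alternative cause is a caveat under *Possible*, sufficient under *Probable*, and excluded under *Definite*. It is more than a clerical slip, because the grade may determine the only safety endpoint, but its consequence is modest. If the investigator's grade feeds the endpoint and *Probable* counts as related, related AEs could be over-counted in both arms, by an amount that cannot be derived from the documents.

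No false difference between arms is expected. This assumes that the grader's blind holds and that AEs of non-device origin arise about equally in the two arms. The claim is about what the text allows; nothing shows that AEs have been misgraded. The ranking of *Probable* above *Possible* is taken from the labels and the order of the list, since the protocol does not state it in words.

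**What to change.** 1. Reconcile *Possible*, *Probable* and *Definite* so that an alternative cause counts against *Probable*. For example: timing relative to device use makes a device cause likely, and neither the subject's illness nor other treatment is a likely explanation. This wording is a suggestion. What the authors meant, whether a dropped negation or another connective, is inference, and the sponsor should confirm it.
2. State in Section 6.4 or the standalone SAP that the safety endpoint uses the investigator's grade and not the subject's Related or Not related answer, and list the grades that count as related.

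The cost is one amended definition with the approvals that Section 10 requires, an update to any ePRO help text that shows the definition, and a blinded re-read of any AE already graded *Probable*. No new field, visit or subject is needed.

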# 15.2.2 Sponsor Responsibilities

All adverse events and device deficiencies will be reviewed by the Sponsor to assess regulatory reporting responsibilities for the event. The Sponsor will maintain records concerning adverse device effects, whether anticipated or unanticipated.

The Sponsor will immediately conduct an evaluation of any unanticipated adverse device effects (UADEs). If it is determined that a UADE presents an unreasonable risk to subjects, the Sponsor will terminate the study or the parts of the study presenting that risk as soon as possible. The results of a UADE investigation will be reported to FDA and to the IRB within 10 working days after the Sponsor first receives notice of the effect. Thereafter, the Sponsor will submit such additional reports concerning the effect as requested by FDA.

### **15.3 ANTICIPATED POTENTIAL ADVERSE EVENTS**

Anticipated potential adverse events (AEs) consist of those related to the investigational medical device or the procedures involved in using the device, as well as AEs that occur in this study's patient population who may be receiving treatment for comorbidities. Anticipated potential AEs that may be encountered in the conduct of this study including potential AEs related to the use of the FW-200 are listed in Section 5.2 *Potential Anticipated Adverse Events*. It is possible that there are additional risks that have not been foreseen.

# **16 VULNERABLE POPULATIONS**

ISO 14155:2020 defines a vulnerable subject as an individual whose willingness to volunteer in a clinical investigation could be unduly influenced by the expectation, whether justified or not, of benefits associated with participation or of retaliatory response from senior members of a hierarchy in case of refusal to participate. Individuals who suffer from Major Depressive Disorder would be considered a vulnerable population and therefore included within this clinical investigation.

These vulnerable subjects according to the ISO 14155 definition will be asked to provide their informed consent if they are capable of providing it themselves and the consent process will be performed without undue delay. Informed consent processes shall be conducted according to national law and IRB procedures.

The protection of the rights and welfare of study participants will be overseen by the responsible IRB and the Principal Investigator.

# 17 SUSPENSION OR PREMATURE TERMINATION OF THE CLINICAL INVESTIGATION

#### **17.1 CRITERIA FOR SUSPENSION OR PREMATURE TERMINATION**

The clinical study may be stopped at any time at the Sponsor's discretion.

In addition, further recruitment in the study may be stopped due to insufficient compliance with the protocol, GCP-related issues, and/or other applicable regulatory requirements, procedure-related problems, lack of enrollment, or if the number of subject discontinuations for administrative reasons is deemed too high.

Version 5.0 08-Jun-2022

#### 17.2 SUBJECT FOLLOW-UP IN THE CASE OF STUDY TERMINATION

In the event of early study termination, all subjects will be contacted via telephone by the Sponsor or designee. A record of contact(s) with each subject will be maintained in the ePRO.

# **18 PUBLICATION POLICY**

Publication policy will be addressed in the Principal Investigator clinical trial agreement.

#### **18.1 CLINICAL TRIAL REGISTRATION**

This study will be registered on www.clinicaltrials.gov per federal regulations. This study is required by the FDA to be registered in the US government database for the registration of clinical trials. Information that can be viewed by all who access the website will only include the study design, the clinicians interacting with subjects in the study, and the study results at the completion of the study. No personal information and no protected health information (PHI) will be entered into the database.

# **20 APPENDICES**

**20.1 APPENDIX 1: DEVICE COMPONENT NAMES, MODEL NUMBERS AND VERSIONS** The FW-200 CES Device consists of the following components:

Component	Part/Model Number
CES device controller	DR-9001
Electrode receptacle with sponge	DR-9010
Electrode lead wires - Red	DR-9009
Electrode lead wires - Black	DR-9008

Headband	DR-9005
Sponge pack (4 sponges)	DR-9010
Velcro headbands	DR-9005
Carry case	DR-9011
User guide	PL 1002
